## 1. Background

 Epidural anesthesia is widely used for cesarean delivery, especially in China. However, due to incomplete block of the splanchnic nerve, parturients often complain discomfort or pain during exploration of the uterus, pulling peritoneum, and fetal delivery. The referred pain brings painful memories and mental stress to parturients, and also affect the conduct of surgical procedure. In some cases, change to general anesthesia is required. Therefore, supplemental analgesics during cesarean delivery under epidural anesthesia is sometimes required and necessary.

Esketamine, a dextrorotatory isomer of ketamine, is two times more potent than ketamine in hypnotic and analgesic effect, with less psychiatric adverse reactions. In a pre-clinical study, Strümper et al. verified that esketamine has similar effects on uterine perfusion, and has limited effects on maternal/fetal hemodynamics and respiration when compared with racemic ketamine; it thus might be an appropriate analgesic in the obstetric setting. In clinical studies, Unlugenc et al. found that adding esketamine (0.05 mg/kg) to intrathecal plain bupivacaine (10 mg) for spinal anesthesia resulted in rapid onset of sensory and motor block and enhanced segmental spread of spinal block in patients undergoing cesarean delivery. Suppa et al. reported that, for women after cesarean delivery, preventive esketamine administration (0.5 mg/kg intramuscular injection at 10 minutes after childbirth, followed by a 2 μg/kg/min intravenous infusion for 12 h) has analgesic effects and was safe.

However, the efficacy and safety of intravenous esketamine before childbirth are still unclear. We therefore try to investigate the sedative and analgesic effects of intravenous esketamine before childbirth during cesarean delivery under epidural anesthesia. We will also explore the placental transfer of intravenous esketamine as well as the effects on maternal and fetal outcomes.

[figure not shown]
# 2. Purpose of the study

The purpose of the study is to investigate the sedative and analgesic effects of intravenous esketamine before childbirth during cesarean delivery under epidural anesthesia.

# 3. Study design

#### 97 3.1 Type of the study

This is a muti-center, randomized, double blind trial with two parallel arms. The flow chart of the study is shown in Figure 1.

102

103

104

105

106107

108

109

#### 3.2 Sample size calculation

Based on a pilot study, we suppose that the mean difference in NRS pain score immediately after fetal delivery (10 min after administering esketamine) would be 0.3 with standard deviations (SD) of 0.85 and 1.23, respectively, between the two groups. With alpha set at 5% and power at 90%, 263 patients will be needed in each group. Considering a drop-out rate of about 10%, we plan to enroll 300 patients in each group. The sample size was estimated with the PASS 15.0 software.

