# 165 5. Randomization and Masking

### 166 5.1 Randomization

- 5.1.1 Random allocations will be generated using the SPSS 22.0 (IBM Corp, Armonk, NY,
- 168 USA) in a 1:1 ratio. Assignments will be concealed in sequentially numbered opaque envelops.
- 5.1.2 For each participating center, a study coordinator will be designated to distribute the
- 170 randomization result to the anesthesiologists according to the sequence of recruited patients,
- and to coordinate between investigators.
- 5.1.3 For each recruited patient, an anesthesiologist will be designated for anesthesia and data
- 173 collection according to the result of randomization.
- 5.1.4 Study intervention (use esketamine or normal saline) will be provided according to the
- randomization results by anesthesiologists who do not participate in the outcome assessments.

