# 329 13.1 General principles

- 330 13.1.1 The primary and secondary outcomes will be analyzed in an intention-to-treat
- population, i.e., all patients are analyzed in the group to which they are randomized. Also, we
- will do per-protocol analysis for the primary endpoints after excluding patients with major
- 333 protocol deviation.
- 334 13.1.2 For continuous variables, the Kolmogorov-Smirnov test will be applied to evaluate the
- distribution. Variables with normal distribution were presented as mean  $\pm$  standard deviation
- 336 (SD). Variables with non-normal distribution will be presented as median and interquartile
- 337 range (IQR).
- 13.1.3 Categorical variables will be presented as number of cases (%).
- 13.1.4 For the primary outcomes, p<0.025 (0.05/2) will be considered statistically significant.
- For other outcomes, two-tailed tests will be used and p<0.05 will be considered to be
- statistically significant unless otherwise indicated after Bonferroni correction.

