#### 355 13.5 Efficacy analysis

356 13.5.1 Evaluation of primary endpoints

- For the primary outcomes (maternal pain intensity and sedation score immediately after fetal
- delivery), the differences between group will be analyzed using Mann-Whitney U test. Median
- differences and 95% CIs will be calculated with the Hodges-Lehmann estimators.
- 360 13.5.2 Evaluation of secondary and other endpoints
- 361 13.5.2.1 Discrete variables (maternal pain intensity and sedation score during the perinatal
- period, neonatal Apgar scores, and umbilical vein pH) will be analyzed with the Mann-Whitney
- 363 U tests. Median differences and 95% CIs will be calculated with the Hodges-Lehmann
- 364 estimators. Missing data will not be replaced.
- 13.5.2.2 Categorical variables (neonatal ward admission proportion) will be analyzed using the
- chi-square tests, continuity correction chi-square tests or Fisher exact tests. The rate differences
- and 95% CIs will be provided. Missing data will not be replaced.
- 368 13.5.2.3 Time-to-event variables (length of hospital stay after surgery) will be analyzed with
- the Kaplan-Meier estimators with differences between groups assessed by the log-rank test;
- Cox proportional hazards models will be used to calculate HRs and 95% CIs.
- 371 13.6 Safety analysis
- 372 13.5.1 Describe the occurrence of adverse events in each group.
- 13.5.2 Describe the management of adverse events when appropriate.
- 374 13.5.3 Describe the occurrence of severe adverse events.
- 375 13.5.4 The rates of adverse events and/or managements between the two groups will be
- compared with Chi-Square test, continuity correction Chi-Square test or Fisher exact test.
- 377 13.5.5 Missing data will not be replaced.

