# 2. Sample size estimation

- Based on a pilot study, we suppose that the mean difference in NRS pain score immediately
- after fetal delivery (10 min after administering esketamine) would be 0.3 with standard
- deviations (SD) of 0.85 and 1.23, respectively, between the two groups. With alpha set at 5%
- and power at 90%, 263 patients will be needed in each group. Considering a drop-out rate of
- about 10%, we plan to enroll 300 patients in each group. The sample size was estimated with
- the PASS 15.0 software.

500

501

502

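### The 90% power stated for pain is computed at alpha 5%, but pain is tested at p<0.025; on the same t-test basis the power is 84% to 89%, depending on how many patients are analysed

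*Combined protocol and SAP*

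**What the plan says.** Protocol 3.2 rests the sample size on one outcome, pain: "we suppose that the mean difference in NRS pain score immediately after fetal delivery (10 min after administering esketamine) would be 0.3". The assumed SDs are 0.85 in one group and 1.23 in the other. The section then concludes: "With alpha set at 5% and power at 90%, 263 patients will be needed in each group". Enrolment follows from that number: "Considering a drop-out rate of about 10%, we plan to enroll 300 patients in each group". SAP section 2 repeats the calculation ("and power at 90%, 263 patients will be needed in each group").

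Protocol 8.1 and SAP 3.1 name two primary outcomes, both taken immediately after fetal delivery: NRS pain and the Ramsay sedation score. Protocol 13.1.4 sets the decision rule: "For the primary outcomes, p<0.025 (0.05/2) will be considered statistically significant". SAP 4.1.4 has the same rule.

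Protocol 13.5.1 and SAP 4.5.1 name the test for both primary outcomes; the protocol's sentence ends: "delivery), the differences between group will be analyzed using Mann-Whitney U test".

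Protocol 4.3 keeps several kinds of drop-out in the intention-to-treat analysis. Protocol 4.4 removes only patients who withdraw consent before the intervention, whose surgery is cancelled, or who have no primary assessment.

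**The concern.** The sample size section and the decision rule use different significance levels. Pain is sized at 5% and judged at 2.5%, and nothing in protocol 3.2 or SAP section 2 reflects the halving. A stricter threshold with the same number of patients means less power, so the stated 90% cannot describe the test as planned. Pain is the only primary outcome with any power statement, so this is the plan's only claim about its chance of detecting the effect it assumes.

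There is a second, smaller gap. The calculation concerns a difference in means, while the analysis is a Mann-Whitney test.

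**Working it through.** **Inputs.** Mean difference 0.3; SDs 0.85 and 1.23; alpha 5%; power 90%; 263 per group; 300 enrolled per group with about 10% loss (all protocol 3.2). Allocation 1:1 (protocol 5.1.1). Threshold for each primary outcome 0.025 (protocol 13.1.4).

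**Step 1: reproduce 263.** By the normal approximation, n per group = (SD₁² + SD₂²)(z₁₋α/₂ + z₁₋β)² / δ².

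- SD₁² + SD₂² = 0.7225 + 1.5129 = 2.2354.
- Two-sided 0.05: 2.2354 × (1.960 + 1.2816)² / 0.09 = 261.0.
- The unequal-variance (Welch) t-test with the noncentral t distribution gives 89.99% at 262 and 90.1% at 263, so 263 is the smallest adequate n. This matches the plan exactly.
- One-sided 0.05 gives 213, which does not match. The plan's 5% is therefore two-sided, although protocol 3.2 does not say so.

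**Step 2: required n at the planned threshold.** Two-sided 0.025: 2.2354 × (2.2414 + 1.2816)² / 0.09 = 308.3, so 309 by the normal approximation and 310 by Welch. With 10% loss, 310 / 0.90 = 344.4, so 345 enrolled per group.

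**Step 3: power with the planned numbers.** By the normal approximation at 263, the standard error is √(2.2354 / 263) = 0.0922 and 0.3 / 0.0922 = 3.254. Then 3.254 − 2.2414 = 1.013, which gives 84.4%. The Welch results are:

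| Analysed per group | Power at two-sided 0.05 | Power at two-sided 0.025 |
|---|---|---|
| 263 (stated requirement) | 90.1% | 84.2% |
| 270 (300 less 10%) | 90.8% | 85.2% |
| 300 (all enrolled) | 93.4% | 89.0% |

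The false-negative risk at the assumed effect is thus 15.8% at 263, 14.8% at 270 and 11.0% at 300, against the 10% implied by the plan.

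**Step 4: the planned test.** Mann-Whitney power depends on the full distribution of the integer scores in each group. The documents give no group means or score frequencies and do not say which SD belongs to which arm. As an illustration only, if scores were normal (relative efficiency 3/π = 0.955), 263 would act like about 251 per group, with power of about 82.6% at 0.025. Real NRS scores are discrete and bounded, so this is not an estimate for this trial.

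**The case against.** **Few patients need be lost.** Protocol 4.3 keeps patients with no intervention, deviation, interruption, prohibited drugs or late withdrawal in the intention-to-treat set, and the outcome is measured about 10 minutes after dosing. The number analysed may be well above 270. This stands. A reader might infer that the power is simply 84-85%, but that holds only at 263-270 analysed; the fair range is 84-89%. Even with no loss it stays below 90%.

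**The 0.025 could be a one-sided level.** Protocol 13.1.4 states two-tailed tests only for the other outcomes. If 0.025 were one-sided, power at 263 would remain 90.2% by the normal approximation. But the plan writes the threshold as 0.05/2, has two primary outcomes, and mentions Bonferroni correction in the same item. An alpha split is the natural reading.

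**Co-primary could mean that both must succeed.** No split would then be needed. The plan does split, and under that reading joint power could not exceed the power for pain alone.

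**The fixed split is valid.** This also stands. Bonferroni controls the family-wise error, and replacing it is a choice rather than a correction.

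**The test mismatch might suggest that true power is far lower.** The documents do not support that. Without the pilot frequencies, Mann-Whitney power could lie on either side of the t-test figure.

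**A null pain result might be taken as showing no effect.** Nothing in the plan says it would be, and protocol 13.5.1 requires Hodges-Lehmann differences with 95% confidence intervals.

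**Conclusion.** The power statement is wrong as written and should be fixed. The number 263 is correctly calculated; the fault is that the sample size section and the decision rule disagree on alpha. On the t-test basis used for sizing, power for pain at two-sided 0.025 is 84.2% at 263, 85.2% at 270 and 89.0% at 300 analysed per group. That is a shortfall of about 1 to 6 percentage points, and 90% would need 310 analysed per group.

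This rests on the plan's assumed difference and SDs, on a two-sided reading of both alpha levels, and on 0.05/2 being an alpha split. It does not mean that type I error is uncontrolled or that the effect estimate is affected. The power of the planned Mann-Whitney test is not established by the documents in either direction, and no power is given for sedation.

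**What to change.** **Needed.** In protocol 3.2 and SAP section 2, state that each primary outcome is tested at two-sided 0.025. Give the power for pain as about 84% at 263, and 84-89% over 263-300 analysed per group. Say that this is a t-test approximation while the planned test is Mann-Whitney; then recompute the power for Mann-Whitney from the pilot NRS frequencies and report it. The cost is wording and one calculation; the stated power becomes less favourable, and no patients are added.

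**Optional, and only if fixed before the unmasking in protocol section 11.** In protocol 13.1.4 and SAP 4.1.4, replace the fixed split with Holm's procedure: test the smaller p-value at 0.025 and, if it is significant, the other at 0.05. Family-wise error stays at 5%, and power is never lower than under the fixed split. If sedation is significant at 0.025, pain is tested at 0.05, where t-test power is 90.1% at 263 and 90.8% at 270. That gain depends on sedation, so it should not be quoted as the unconditional power for pain.

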## 119 4. Study participants

- Potential participants will be screened before surgery by the qualified investigators.
- 121 4.1 Inclusion criteria
- 4.1.1 Women aged 18 years or older.
- 4.1.2 Full-term single pregnancy.
- 4.1.3 Scheduling for elective caesarean delivery.
- 4.1.4 Planning for epidural anesthesia.
- 4.1.5 Agree to participate, and give signed written informed consents
- 127 4.2 Exclusion criteria
- Patients will be excluded if they meet any of the following criteria:
- 129 4.2.1 Body mass index (BMI)  $\geq$ 27 kg/m^2.
- 4.2.2 Previous mental illness; central nervous system disease; liver disease, abnormal kidney
- function; abnormal heart and lung function; diabetes; American Society of Anesthesiologists
- 132 (ASA) classification III or above.
- 4.2.3 Severe obstetric complications, such as preeclampsia and eclampsia, pregnancy-induced
- hypertension, placenta previa, or placental abruption.
- 4.2.4 Stillbirth, neonatal malformation.
- 4.2.5 Contraindications to epidural anesthesia, including abnormal coagulation function, taking
- anticoagulant therapy, severe hypovolemia, or hemodynamic instability.
- 138 4.3 Criteria of drop-out
- 139 4.3.1 Study intervention is not administered (change to general anesthesia) or protocol
- 140 deviation occurs.
- 4.3.2 Intervention interrupted by the investigators/anesthesiologists (due to adverse events).
- 142 4.3.3 Use of a prohibited drugs.
- Details of the above situations should be recorded and corrected when possible. The cases will
- be followed up according to the study protocol and included in the intention-to-treat analysis.
- 4.3.4 Withdraw consent after intervention started.
- The situation should be recorded. The primary therapeutic effects recorded in the last time will
- be regarded as the final assessment results. The cases will be included in the intention-to-treat
- 148 analysis.
- 149 **4.4** Criteria of elimination
- Enrolled patients will be excluded if they meet any of the following criteria:

- 4.4.1 Withdraw consents before intervention.
- 4.4.2 Surgery cancelled.
- 4.4.3 No assessment result of the primary outcomes.
- The causes of elimination should be explained. The case will be excluded from the intention-
- to-treat analysis. The case report forms will be preserved for reference.

# 156 4.5 Criteria of study interruption

- 157 Study will be interrupted in the following situations:
- 4.5.1 Severe safety problem occurred during the study.
- 4.5.2 Serious mistake found in the protocol.
- 4.5.3 Fund or management problem of the investigators.
- 4.5.4 Study cancelled by the administrative authority.
- Study interruption may be transient or permanent. All recorded case report forms will be
- preserved for reference in case of study interruption.

# 164

# 165 5. Randomization and Masking

### 166 5.1 Randomization

- 5.1.1 Random allocations will be generated using the SPSS 22.0 (IBM Corp, Armonk, NY,
- 168 USA) in a 1:1 ratio. Assignments will be concealed in sequentially numbered opaque envelops.
- 5.1.2 For each participating center, a study coordinator will be designated to distribute the
- 170 randomization result to the anesthesiologists according to the sequence of recruited patients,
- and to coordinate between investigators.
- 5.1.3 For each recruited patient, an anesthesiologist will be designated for anesthesia and data
- 173 collection according to the result of randomization.
- 5.1.4 Study intervention (use esketamine or normal saline) will be provided according to the
- randomization results by anesthesiologists who do not participate in the outcome assessments.

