## 176 **5.2 Masking**

- 5.2.1 All patients, anesthesiologists, other health care team members, and investigators who
- are responsible for data collection and follow-ups will be blinded to group allocation.
- 5.2.2 Investigators who are responsible for postoperative follow-up and outcome assessments
- are not involved in anesthesia and perioperative management and have no knowledge of study
- 181 group assignment.
- 5.2.3 Statistical analysis will be performed by an independent statistician.

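### The randomization section passes the allocation to anesthesiologists whom the masking section calls blinded, and no one is named to score the co-primary outcomes in theatre

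*Combined protocol and SAP*

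**What the plan says.** Protocol 5.1 (Randomization) describes who handles the allocation:

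- 5.1.2: a coordinator at each center distributes the "randomization result to the anesthesiologists according to the sequence of recruited patients".
- 5.1.3: "For each recruited patient, an anesthesiologist will be designated for anesthesia and data", continuing "collection according to the result of randomization".
- 5.1.4: esketamine or saline is provided according to the "randomization results by anesthesiologists who do not participate in the outcome assessments".

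Protocol 5.2 (Masking) describes who is blinded:

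- 5.2.1: "All patients, anesthesiologists, other health care team members, and investigators who", continuing "are responsible for data collection and follow-ups will be blinded to group allocation". No exception is made for whoever provides the drug.
- 5.2.2: "Investigators who are responsible for postoperative follow-up and outcome assessments", continuing "are not involved in anesthesia and perioperative management and have no knowledge of study" group assignment.

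Protocol 8.1 and SAP 3.1 make NRS pain and Ramsay sedation immediately after fetal delivery co-primary. Both are recorded during surgery, under 7.2.3 and 7.2.4 of the Data collection section, and no assessor is named. Section 6.1.6 requires the same volume of saline as esketamine. It says nothing about who prepares the syringe, how it is labelled or how it looks.

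**The concern.** The trial is described as double blind, and both co-primary outcomes are scored in theatre. Ramsay sedation is an observer's rating. NRS pain is the patient's own report, but a member of staff elicits and records it. If the person scoring knows the arm, expectation can shift the scores, and the analysis cannot undo that once the data are collected. The planned NRS difference is only 0.3 points, so even a small shift is large relative to the effect sought. Several centers take part, and each could settle the conflicting text differently. Monitoring under 14.2.4.4 must verify the randomization procedure, but here it has no single procedure to verify against.

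**Working it through.** **Comparison of the sections**

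1. *Does any anesthesiologist know the allocation?* Yes under 5.1.2, which hands them the result, and under 5.1.4, which has them act on it. No under 5.2.1, which lists anesthesiologists as blinded without exception. These statements conflict directly.
2. *Does the person collecting data know the allocation?* Section 5.1.3 ties the anesthesiologist who collects data to the randomization result. Section 5.2.1 says those who collect data are blinded. As worded, these also conflict.
3. *Does 5.1.4 settle it?* It keeps those who provide the drug away from outcome assessment. It does not mention the anesthesiologist of 5.1.3, and it confirms that some anesthesiologists act on the allocation.
4. *Does 5.2.2 settle it?* If postoperative qualifies both follow-up and outcome assessments, scoring at delivery is not covered. If it qualifies follow-up only, scoring at delivery is covered, but then the assessors cannot be involved in anesthesia. That conflicts with 5.1.3 if data collection there includes the scores.
5. *Is the intraoperative scorer named elsewhere?* No. Neither 7.2, 8.1 nor the SAP names one.

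**The plan's own sample size**

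Inputs from protocol 3.2: difference 0.3, SDs 0.85 and 1.23, two-sided alpha 5%, power 90%.

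- Sum of variances: 0.85² + 1.23² = 0.7225 + 1.5129 = 2.2354.
- n per group = (1.9600 + 1.2816)² × 2.2354 / 0.3² = 10.508 × 24.838 = 261. The plan states 263, so the figure reproduces closely.
- 263 / 0.90 = 292.2, so 293. The plan enrolls 300.

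**Illustration of what a scoring bias could do**

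From the plan: the SDs above; 300 × 0.90 = 270 analyzed per group; significance level 0.025 (protocol 13.1.4), two-sided critical value 2.2414. Assumed: no true effect, and a bias b of 0.1 or 0.2 NRS points between arms.

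- SE = √(2.2354 / 270) = 0.0910.
- False-positive rate = 1 − Φ(2.2414 − b/SE) + Φ(−2.2414 − b/SE).
- b = 0.1: b/SE = 1.099; 1 − Φ(1.142) + Φ(−3.340) = 0.1267 + 0.0004 = 0.127.
- b = 0.2: b/SE = 2.198; 1 − Φ(0.043) = 0.483, the second term being negligible.

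With 263 per group the same formula gives 12.4% and 47.1%. No comparable figure is given for Ramsay, because the documents state no SD for it.

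**The case against.** The strongest reply is that the intent is plain. Section 5.1.4 keeps those who provide the drug out of outcome assessment, and 5.2.1 blinds data collectors. Two anesthesiologists per patient, one providing the drug and the other blinded and collecting data, would reconcile 5.1.3 with 5.1.4. Data collection in 5.1.3 need not mean outcome scoring, since 7.2 also lists durations, fluids and vasopressors. Section 5.2.2 may already cover every outcome assessment.

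Much of this stands as to intent. A reader might infer that the protocol instructs an unblinded anesthesiologist to score the primary outcomes. The documents do not support that: 5.1.4 and 5.2.1 both forbid it. But the two-person arrangement is never stated, 5.1.3 still links the data collector to the randomization result, and 5.2.1 still calls all anesthesiologists blinded.

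A reader might also infer that knowledge of the arm would influence epidural top-ups. The support for that is weak: 6.2.2 ties added epidural drug to block level, and 6.1.6 gives study drug only after the target level is reached.

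It is also fair to object that the arithmetic rests on assumed biases, compares means where 13.5.1 plans a Mann-Whitney test, and models the less exposed of the two outcomes.

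**Conclusion.** The contradiction between 5.1.2 to 5.1.4 and 5.2.1 is literal and should be corrected. Its consequence is limited: the text leaves open, without requiring it, that someone who knows the arm scores the co-primary outcomes. Ramsay is the more exposed; the NRS is less so because the blinded patient reports it.

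The rates of about 13% and 48% show how sensitive a trial planned around a 0.3-point difference would be to biases of 0.1 and 0.2 points. They depend on those assumed biases, no true effect, 270 per group and a normal approximation. They neither estimate the bias in this trial nor show that the wording causes any. The contradiction holds without them.

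**What to change.** - **5.1.3:** in "collection according to the result of randomization", delete everything after the first word.
- **5.1.2 and 5.1.4:** state that only the person who opens the envelope and prepares the study drug knows the allocation, and that this person takes no part in anesthetic care or scoring.
- **Handover:** have the study drug passed on in coded syringes of identical volume and appearance. Otherwise, list the drug provider as an explicit exception in 5.2.1.
- **5.2.2:** extend it to surgery, so that whoever records intraoperative NRS and Ramsay has neither seen the allocation nor prepared the drug.

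The cost is a wording change and a preparation step for a suitably qualified person within the roles that 5.1.4 already separates. The documents do not show that the center coordinator is qualified to prepare study drug, so that person has to be identified. Sample size, outcomes and analysis are unchanged.
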